**AME00156146:**

We are required by the study funder (NCCIH) to screen for adverse events after the intervention. An adverse event questionnaire has been added to Section 29 of the IRB application to help our team identify adverse events (AE) and severe adverse events (SAE). This screener will be performed 7 – 10 days following the intervention. This can be delivered digitally, with a follow-up phone call if our team requires additional information from the participant or if the participant is unresponsive. Pain assessments taken at intake will also be reassessed during the screener.

The PI will maintain an adverse event log to grade the severity, study intervention relationship, action taken regarding study participation, outcome of the AE, expectedness, and SAE grading, along with the participant ID# and investigators initials and date of logging.

The potential risks of this project are anticipated to be no more than minimal risk with essential safeguards to protect the welfare of study participants. Only Adverse Events related to the study procedures (e.g., ultrasound imaging, myofascial massage) will be assessed for grade/attribution and recorded in the study database. These adverse events will be reported in aggregate form in conjunction with the completion of an annual continuing review application with the University of Michigan IRB board.

\*\*\* Begin **Ame00163783** \*\*\*

The potential risks of this project are anticipated to be no more than minimal risk with essential safeguards to protect the welfare of study participants. Only Adverse Events related to the study procedures (e.g., ultrasound imaging, myofascial massage) will be assessed for grade/attribution and recorded in the study database. These adverse events will be reported per the standard IRB-HSBS reporting guidance.

\*\*\* End **Ame00163783** \*\*\*

Per current institutional guidelines, the research team must report any serious adverse events resulting in death, life-threatening outcomes, hospitalization, or significant disability/permanent damage to the local IRB within seven calendar days of becoming aware of the event. Serious adverse events unrelated to the study procedures will be reported in aggregate form in conjunction with the completion of an annual continuing review application.

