After baseline measurements are completed, participants will be taken to the massage room where they will meet the massage therapist. Participants will be asked to remove all upper body clothing before lying down face up on the massage bed. They will be asked to cover their bodies, including chest and shoulders, with a sheet and woolen blanket. The massage therapist will leave the room while the participants get ready. Once the participant is ready, the massage therapist will re-enter the room and begin the myofascial massage. The treatment will last 30 minutes and focus on the chest and shoulder of the side that received the cancer treatment. Techniques applied during the intervention will include skin glide (variable time), stroking (2-3 minutes), scar tissue rolling (2-3 minutes), strumming (2-3 minutes), fascial stretch (3-5 minutes), circular friction (1-2 minutes), deep fascial release (3-5 minutes) and arm pull (60 seconds). The timing and order of each element will be varied based on tissue response and patient feedback. The massage therapist will carefully expose areas of the chest and/or shoulder to perform the treatment. A massage oil may be applied to the participant's skin if necessary. After the conclusion of the massage treatment, the massage therapist will leave the room so that the participant can get dressed again. No research personnel will be present in the massage room during the entire time.

Immediately afterward, participants will return to the examination room, where the measurements conducted at baseline will be repeated. Participants will then remain in the clinical suite (or an adjacent waiting room) for 60 minutes, after which all measurements will be repeated a second time. During their 60-minute wait period, participants will be asked to fill in the treatment satisfaction questionnaire. Additionally, participants will be allowed to keep themselves occupied (e.g., reading), and they will be allowed to use the TV entertainment system provided in the examination room.

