This experiment carries a small (\$30) nominal payment that is not contingent upon successful completion of the study. Compensation will be in the form of a gift card. This study provides a small direct benefit to the participants resulting from the massage treatment. Risks associated with the treatment intervention are no more than minimal and include mild soft tissue discomfort during the massage treatment and possible muscle soreness the next day. To avoid/minimize discomfort during the treatment, the massage therapist will adjust the treatment accordingly. For participants that withdraw early, we will prorate this payment at \$15 per hour, rounded to the nearest 20-minute interval, up to a maximum payment of \$30.

All data will be stored by randomized study ID for each participant. All data collected during the appointment will be kept in a secure U-M database. There will be one document linking the ID numbers to the identifiers, which will be kept in a locked cabinet within a card-locked laboratory or key-locked office. Only members of the study team will have access to the document. This will be kept for 12 months after the study is completed, as it may be needed during the analysis of the data. Twelve months after the conclusion of the study, all identifiable information will be destroyed.

\*\*\* Begin **Ame00163783** \*\*\*

All data will be stored by randomized study ID for each participant. All data collected during the appointment will be maintained in REDCap, which is password-protected, with only the study team members able to access identifiable information. There will be one document linking the ID numbers to the identifiers, which will be kept in a locked cabinet within a card-locked laboratory or key-locked office. Only members of the study team will have access to the document. This will be kept for 12 months after the study is completed, as it may be needed during the analysis of the data. Twelve months after the conclusion of the study, all identifiable information will be destroyed.

\*\*\* End **Ame00163783** \*\*\*

All data collected during the research, including self-reported information from breast cancer survivors about their diagnosis and treatment, will be saved only under their randomized study ID. Data will be stored on password-protected devices inside a card-locked laboratory and separate from any documents containing any personally identifiable information.

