There are some potential risks to this experiment. There may be some discomfort from the ultrasound transducer indenting the skin. We expect the risk probability of this to be infrequent and the risk severity to be minor. To mitigate this risk, researchers will inform the participant prior to applying the transducer to skin and consistently ask participant if they are comfortable. There is also a small risk of an allergic reaction to the massage oil, if applied. We will minimize this risk by only using massage oil if necessary and asking the participants about known allergies before doing so. If an allergy may exist, we will not use massage oil. Finally, there is a minor risk of soreness and discomfort in the massaged regions which will subside within two days of treatment.

Loss of confidentiality is expected to be rare but is of major seriousness. To minimize the risk of loss of confidentiality, only authorized research personnel will have access to the data. Coded identifiers will be used, with a list housed within a locked cabinet inside of a secure office. This list includes name, subject ID, height, weight, and ethnicity as this information may be necessary covariates to include within our data analysis. PHI will not be written on paperwork and will be saved on separate from devices where research data is collected and stored. Paperwork will be shredded, and devices will be permanently destroyed or securely wiped 12 months after study completion.

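### The only scheduled adverse-event query is at day 7–10, although every named physical risk with a stated timing arises at the visit or is over within two days

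*Combined protocol and SAP*

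**What the plan says.** AME00156146, placed after the objectives table in Section 6, adds a funder-required screen for adverse events. The instrument is held elsewhere: "An adverse event questionnaire has been added to Section 29 of the IRB application". Its timing is given once: "This screener will be performed 7 – 10 days following the intervention". On mode, the text says "This can be delivered digitally, with a follow-up phone call if our team requires additional information from the participant", and a call is also allowed if the participant does not respond. The intake pain assessments are repeated at the same contact. For recording, "The PI will maintain an adverse event log to grade the severity", together with relationship to the intervention, expectedness and outcome. No times for entering events in that log are given. Only events related to study procedures are to be graded and recorded.

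The physical risks are described in Section 4, Experimental Design. One paragraph says that the treatment risks "include mild soft tissue discomfort during the massage treatment and possible muscle soreness the next day". A later one adds discomfort from the ultrasound transducer and a possible allergic reaction to massage oil, and says "there is a minor risk of soreness and discomfort in the massaged regions which will subside within two days of treatment".

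The account of the visit, also in Section 4, contains no adverse-event form. After the massage the ultrasound measurements are repeated, and during the 60-minute wait "participants will be asked to fill in the treatment satisfaction questionnaire". Staff are to keep checking comfort during imaging, and the therapist is to adapt the massage to limit discomfort. Both are given as ways to reduce risk, and neither is linked to the log. No research staff are in the massage room.

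**The concern.** The trial expects mild, short-lived events, and its one scheduled query comes after they should be over. Whether such an event is reported, and with what onset, duration and severity, then depends on memory.

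Three features of this trial make that matter more than usual.

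- Only procedure-related events are recorded, so attribution leans on timing. Participants are enrolled because they already have upper-quadrant pain, and a week later brief soreness from the massage is harder to separate from the existing pain.
- Discomfort could plausibly differ by arm. The therapist asks for feedback and adjusts technique in the communication-permitted arm, and limits responses in the restricted arm.
- Participants receive a letter disclosing their group once they have completed the visit. If it is handed over as they leave, the only scheduled query reaches people who may know their allocation.

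At stake are the completeness and dating of the safety summary, not the primary analysis of shear wave velocity.

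**Working it through.** The plan gives no figure on this point to reproduce, so the check is date arithmetic on its own timings. The day of the massage is day 0.

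Inputs: screener on day 7 to day 10 (AME00156146); massage and transducer discomfort on day 0, possible soreness on day 1, soreness gone by day 2 (Section 4, risk descriptions).

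Formula: gap = screener day − day on which the harm occurs or has resolved.

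| Named risk | Reference day | Shortest gap | Longest gap |
|---|---|---|---|
| Discomfort during massage | 0 | 7 − 0 = 7 | 10 − 0 = 10 |
| Transducer discomfort | 0 | 7 − 0 = 7 | 10 − 0 = 10 |
| Soreness, when felt | 1 | 7 − 1 = 6 | 10 − 1 = 9 |
| Soreness, once resolved | 2 | 7 − 2 = 5 | 10 − 2 = 8 |
| Reaction to massage oil | not stated | cannot be computed | cannot be computed |

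The rows measure different things. For events at the visit the gap runs from occurrence; for soreness the most favourable gap runs from resolution. Even on that reading it is at least 5 days.

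Next, is there an earlier route into the log? Going through the visit in order:

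- Imaging: comfort is asked about; no recording is described.
- Massage: the therapist is alone with the participant; no hand-over to the log is described.
- 60-minute wait: the satisfaction questionnaire is the only form described.
- Second repeat of the ultrasound measurements: no adverse-event question is described.
- After the visit: nothing until day 7.

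The log could accept a spontaneous report at any of these points, but no step prompts one.

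On scale: with 30 participants, each person whose event goes unreported lowers the reported proportion by 1/30 = 3.3 percentage points. Within an arm, if the 1:1 split is exact, it is 1/15 = 6.7 points. How many would go unreported cannot be derived from the documents.

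**The case against.** The case for leaving the plan alone has real content. A look-back at day 7–10 covers the whole two-day risk period and can also catch delayed or persisting events, which an earlier query cannot. The study is described as no more than minimal risk, adverse events are not an endpoint in Section 6, and the stated aim is a screen after the intervention. The questionnaire may ask for onset and end dates and set a clear recall period; the documents do not show it. This is why the screener should stay and why no amount of under-reporting can be claimed. It does not remove the reliance on memory for events already over.

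A reader might infer more than the documents support, in four ways.

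- That every physical risk is over before the screener. The oil reaction has no stated onset or duration and could still be present at day 7–10.
- That nothing is asked at the visit. Comfort is checked during imaging, and the therapist seeks feedback in the permitted arm. What is missing is a described recording step.
- That the two accounts of soreness conflict. The first, "mild soft tissue discomfort during the massage treatment and possible muscle soreness the next day", says when soreness may be felt; the second says when it will have gone. Soreness on day 1 that has cleared by day 2 fits both.
- That the trial will under-report. The documents support only that it may.

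There are also fair objections to obvious remedies. Adverse-event items placed beside the satisfaction form could influence a secondary endpoint. Therapist notes would be gathered unequally, since the therapist solicits feedback in one arm only, and could hint at allocation to blinded staff. The order and source of the added items need to answer both.

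**Conclusion.** The concern holds for every named physical risk with a stated timing. The single scheduled adverse-event query comes 7–10 days after events at the visit and 5–8 days after soreness should have resolved, and no earlier step is described that puts such events in the log. Mild events may be missed or misdated.

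This rests on the risk timings in Section 4 being a fair account of what is expected, and on there being no adverse-event form at the visit beyond what the document describes. If the unseen IRB material includes one, the point largely falls away. It is a cheap improvement to safety ascertainment; the primary outcome, the sample size and the planned analyses are unaffected.

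**What to change.** Keep the day 7–10 screener for late or persisting events, and add two contacts.

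- **End of visit.** Ask the same short participant-reported adverse-event items in both arms, after the satisfaction questionnaire and the last ultrasound measurement and before the allocation letter is handed over. Enter the answers in the adverse-event log. This order protects the satisfaction score and the imaging, and obtains the answers before participants learn their group.
- **About day 2–3.** Send the same digital questionnaire once, recording onset and end of any soreness, so that the two-day expectation can be compared with near-contemporaneous data.

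Do not make therapist notes the main source, because feedback is solicited only in the communication-permitted arm.

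The cost is one amendment, a few minutes at the visit and one more digital message for each of 30 participants, with no extra visit or staff. The count of mild events will probably rise, and the report should say that they were solicited.

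### The adverse-event rule makes relatedness a precondition for assessing relatedness, and it contradicts the investigator's log in the same section

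*Combined protocol and SAP*

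**What the plan says.** The adverse-event text follows the endpoint table in section 6 (Objectives and Endpoints) and opens with the AME00156146 label. It sets five rules.

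- **Screening.** "We are required by the study funder (NCCIH) to screen for adverse events after the intervention", and on timing, "This screener will be performed 7 – 10 days following the intervention". Nothing limits the screener to related events.
- **Log.** "The PI will maintain an adverse event log to grade the severity, study intervention relationship". The same sentence adds action taken, outcome, expectedness and a serious-event grading.
- **Database.** "Only Adverse Events related to the study procedures (e.g., ultrasound imaging, myofascial massage) will be assessed for grade/attribution and recorded in the study database".
- **Listed serious events.** "the research team must report any serious adverse events resulting in death, life-threatening outcomes, hospitalization, or significant disability/permanent damage to the local IRB", with the time limit "within seven calendar days of becoming aware of the event".
- **Unrelated serious events.** "Serious adverse events unrelated to the study procedures will be reported in aggregate form", alongside the annual continuing review.

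The database sentence stands both in the AME00156146 text and in the Ame00163783 text that follows it. The later amendment alters only how the recorded events are reported to the IRB.

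**The concern.** The database sentence uses relatedness as the gate to the step that is supposed to establish relatedness. Someone must therefore form a view on relationship before any event is graded or attributed. The document names no role, gives no criteria and requires no record for that first view.

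At stake is whether the safety data are complete and can be traced. The screener exists because the funder requires it. If an ungraded opinion decides which of its reports reach the database, a reader of the final data cannot tell an event that did not occur from one that was set aside. The text also gives two instructions for the same event, one under the log and one under the database rule, so two people following the protocol could produce different records.

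**Working it through.** The plan states no figure on this point and no arithmetic applies. The check sets the rules side by side.

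**1. Is the sentence current?** Yes. It is repeated word for word inside the Ame00163783 markers. Only the following sentence differs: annual aggregate reporting is replaced by the IRB's standard reporting guidance. The restriction is not superseded.

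**2. Is it circular?** Let R be the judgement that an event is related to the study procedures. Attribution is the act of deciding R. The sentence says that attribution is carried out only if R already holds. An event for which R is undecided, which is every event when first reported, has no route into the assessment except through an earlier, unspecified decision on R.

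**3. Does it agree with the log?** No. The log grades severity and relationship with no relatedness limit. The database sentence confines grading and attribution to related events. The word *only* governs the assessment as well as the database entry.

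**4. Does it agree with the unrelated-serious-event rule?** Poorly. That rule needs a set of serious events already classed as unrelated. Such a set can be formed only by attributing events that the database sentence excludes from attribution.

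**5. What happens to each kind of event if the text is followed literally?**

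| Event | Study database | Log | Reporting route in this text |
|---|---|---|---|
| Non-serious, taken as related | Entered | Yes | IRB standard guidance |
| Non-serious, pre-judged unrelated | Not entered | Possible; scope not stated | None given |
| Serious with a listed outcome, related | Entered | Yes | Seven calendar days |
| Serious with a listed outcome, unrelated | Not entered | Possible; scope not stated | Both seven days and annual aggregate |

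The second row is where a record can be lost: no rule other than the log would hold the event.

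**6. Do the two serious-event sentences agree?** Not as worded. The seven-day sentence covers *any* serious event with a listed outcome and sets no relatedness condition. The next sentence sends unrelated serious events to the annual aggregate. An unrelated hospitalisation falls under both. This concerns the reporting route and is separate from the recording problem.

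**The case against.** The best defence is that the text describes two records. On that reading every event goes into the log, where relationship is graded, and only the related ones are copied to the database. This is workable, and it answers part of the concern.

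- **Events are never recorded.** A reader might infer this, but the documents do not support it. The restriction on recording applies to the study database, and the log could hold the rest.
- **The annual list of unrelated serious events cannot be produced.** This does not follow either. The log has a serious-event grading and could supply the list.

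The defence does not remove the contradiction. The document nowhere states the two-record reading, and the sentence restricts assessment as well as database entry, while the log grades without that restriction.

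Other points on that side also stand. Sections 5 and 6 plan no comparison of adverse events between groups. Section 4 limits knowledge of allocation to the coordinator and the therapist and blinds other data-collection and analysis staff. The intake pain measures are repeated at the screener, so pain at that time is captured whatever happens to the adverse-event entry. Section 4 also names soreness in advance as a risk of the massage, which makes it a poor example of an event likely to be set aside. The questionnaire sits in the IRB application and the reporting guidance is external. Relatedness criteria may exist there, so the absence noted above is an absence from this document only.

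Finally, the two serious-event sentences can be read as a general rule followed by an exception. That is plausible, but the text does not say so, and *any* points the other way.

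**Conclusion.** The point holds in a limited form. The database sentence is current, circular, inconsistent with the log and poorly matched to the unrelated-serious-event rule. Its practical effect is that non-serious events judged unrelated in advance are kept out of the study database, with the log as their only possible record.

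The size cannot be given: the documents state no adverse-event rate and no proportion likely to be judged unrelated, and any figure would be invented. The effect is confined to whatever events the 30 participants report.

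A reader might go further and infer that the arms are compared unfairly. The documents do not support that. Bias between arms would need filtering that differs by arm, nothing in the text shows it, and no such comparison is planned. No endpoint, test or sample size is affected. This is a defect in the safety record that should be corrected, and it does not threaten the primary analysis.

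The conclusion assumes that the sentence is applied as written and that no document outside this one overrides it.

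**What to change.** Replace the database sentence, in effect, with: *All adverse events reported at the visit or on the 7–10 day screener are entered in the log and the study database, and are then graded for severity and attribution. Relationship determines the reporting route, not whether the event is recorded.* State in the log sentence that the log covers all reported events.

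Separately, reconcile the seven-day sentence with the annual-aggregate sentence, so that each type of serious event falls under one stated rule. Which rule applies is for the sponsor and the IRB to settle.

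The cost is a short amendment and a few more rows in a log and database for 30 people. The screener and the log already exist, so no visit, procedure or analysis is added. The gain is safety data that are complete and consistent with the protocol's own rules.
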